In Aim 3 we develop individualized estimates of sociability, activities and sleep. We will aggregate daily mobile data on a weekly basis to predict behavioral measures that are also obtained weekly. Summary statistics such as mean, variance, min, or max will be used for aggregation as deemed appropriate. We will then employ various machine learning algorithms to build, train, and select prediction models for each of the patient behavioral assessment domains using features of sensor and phone utilization data (Table 1). Model development will proceed in three stages. First, we will utilize methods of unsupervised learning to cluster sensor and phone utilization data and extract features to reduce the dimensionality. Second, we will explore a number of supervised learning procedures to build candidate prediction models for patient behavioral assessments. Finally, we will use cross-validation to estimate the out-of-sample performance of the prediction models, and to select best model(s) from among the candidates.

To reduce the number of features upon which to build the prediction models, while preserving the maximum amount of information, the first strategy is to use principal component analysis (PCA). PCA reduces the dimensionality of a data set by identifying linear combinations of the features, the principal components, which maximize variability while remaining mutually uncorrelated. Building the models using fewer candidate features reduces the risk of overfitting, and using the principal components in place of the original features prevents problems of multicollinearity. The second dimension reduction strategy is to use FDR (false discovery rate) threshold. FDR-based thresholding gives an optimal way of adapting to unknown sparsity (only a small number of effects are significantly large) and may be viewed as an estimation procedure with an appropriate penalization scheme accounting for the number of selected variables.

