Given the reduced number of features, various supervised machine learning algorithms will be used to train prediction models for patient behaviors and symptoms. At the preliminary analysis stage, a set of supervised learning algorithms will be explored to evaluate cross-sectional associations between mobile data features and patient behavioral assessments, with the goal of narrowing down the pool of candidate predictors. First, we will consider random forests. A random forest is a collection of decision trees, each built using a random sample of features, and trained on a bootstrap sample from the original data. Random forests are useful for identifying complex interactions among features due to the use of decision tree learning, while protecting against overfitting by means of bootstrap aggregation. Second, we will consider support vector machines (SVM). SVM is a method of supervised learning which classifies instances into categories by estimating a hyperplane that separates instances belonging to different classes. SVM may be used if the outcomes of interest, behaviors and symptoms, can be meaningfully categorized (e.g., high vs. low). Selected predictors from these approaches will be used in the next step of the model building process that takes into account the temporal correlation and time series nature of mobile data and patient assessments. We will use hidden Markov models to predict patients' current behaviors and symptoms based on current features and past patients' behaviors and symptoms. We view patients' features as observed states, and patients' behaviors and symptoms are hidden states that enjoy the Markov property. We will also use linear or generalized linear mixed effects models to predict patient behavioral assessments using selected features from the preliminary stage, while taking into account within-patient correlation in repeated measurements over time.

Models developed using supervised machine learning methods will be evaluated in terms of out-of-sample predictive performance using leave-one-out cross-validation (LOOCV). For time series modeling, models will be trained on times 1, ..., t-1, and evaluated on time t, for each time t. For cross-sectional modeling, models will be trained on all but patient i, and evaluated on patient i, for each patient i. Performance will be averaged across hold-out times/patients to obtain a LOOCV estimate of

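### One leave-one-out cross-validation both picks the Aim 3 model and reports its error, and the outcome-based predictor screen is not stated to be inside the folds

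*Combined protocol and SAP*

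**What the plan says.** All of this is in the Data Analyses section of the combined protocol and SAP, under Aims 3 & 4.

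- **Unit of analysis.** "We will aggregate daily mobile data on a weekly basis to predict behavioral measures that are also obtained weekly".
- **Feature reduction.** Unsupervised clustering and principal components come first, with a false discovery rate (FDR) threshold as a second strategy. Supervised learning follows: "Given the reduced number of features, various supervised machine learning algorithms will be used to train prediction models".
- **Outcome-based screen.** Random forests, and possibly SVM, are used at a preliminary stage to "evaluate cross-sectional associations between mobile data features and patient behavioral assessments", "with the goal of narrowing down the pool of candidate predictors". The survivors move on: "Selected predictors from these approaches will be used in the next step of the model building process". That next step covers hidden Markov models and mixed models.
- **Evaluation.** There are two leave-one-out schemes. "For cross-sectional modeling, models will be trained on all but patient i, and evaluated on patient i, for each patient i". For time series, "models will be trained on times 1, ..., t-1, and evaluated on time t, for each time t".
- **Two roles for one estimate.** "Finally, we will use cross-validation to estimate the out-of-sample performance of the prediction models, and to select best model(s) from among the candidates". The text then calls the averaged leave-one-out performance the estimate of generalization error, and takes as the selected model the one with the smallest such mean squared error.

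No inner and outer loop, reserved test set or external sample is described. Nothing says whether the screen or the FDR threshold is redone when a patient or time point is held out.

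**The concern.** There are two separate problems.

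1. **Selection.** This one is explicit. The smallest of several noisy error estimates is, on average, below the true error of the model it selects. Using that minimum as the generalization error makes the chosen model look better than it is.

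2. **Screening.** This one depends on how the plan is carried out. If the forest/SVM screen is run once on all patients, each held-out patient has already helped to choose the predictors on which that patient is then tested. The held-out error is no longer out of sample. The principal components step does not use the outcome and is not at issue. The FDR threshold adds to the problem only if it tests features against the assessments, which is not stated.

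The main Aim 3 result is how well phone data estimate sociability, activity and sleep. Leave-one-patient-out error is the version that speaks to use in a new Veteran, and it is the version exposed to the second problem. The plan sets no pass mark for cross-validated accuracy (the correlation of 0.50 is a power input). The risk is therefore overstated performance, not a false declaration of success.

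**Working it through.** **The plan's own figures.** It states no cross-validated error. The only figures that can be reproduced are the power statements, using Φ(atanh(r)·√(n−3) − 1.96) with n = 100 × (1 − 0.30) = 70:

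- r = 0.50: 0.5493 × 8.185 − 1.96 = 2.54, power 99.4% (stated: over 95%).
- r = 0.35: 0.3654 × 8.185 − 1.96 = 1.03, power 84.9%, or 85.5% by simulating the t-test (stated: over 85%).

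These stand, and this point does not touch them.

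**Inputs for the simulation.** From the documents: 70 patients; weekly records over 9 months, so 9 × 52/12 = 39 each. Table 1 lists 8 phone inputs for activities, 9 for sleep and 11 for sociability. Four summary statistics are named (mean, variance, min, max), so the largest domain has 11 × 4 = 44 features before reduction. Assumed: independent normal features, intraclass correlation (ICC) 0.3, 0.6 or 0.8 in features and outcome, 5 predictors kept, ordinary least squares, leave-one-patient-out scoring. R² = 1 − (leave-one-out MSE)/(outcome variance).

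**Selection.** Optimism is the true MSE minus the leave-one-out MSE of the winner, less the average of that gap over all candidates. The candidates were linear (principal components, ridge, in-fold screened regression, soft threshold). Ranges cover noise and weak signal, with pools of 15 and 44; 80 runs.

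| Candidates | ICC 0.3 | ICC 0.6 | ICC 0.8 |
|---|---|---|---|
| 4 | 0.003–0.007 | 0.019–0.035 | 0.026–0.067 |
| 12 | 0.006–0.013 | 0.034–0.064 | 0.058–0.096 |

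A separate simulation with 4 candidates gave about 0.006–0.064 in MSE (outcome variance 1).

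**Screening, no true signal.** Entries are for ICC 0.3 / 0.6 / 0.8; 120 runs for the correlation screen and 47 for the forest screen.

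| Pool and screen | r, screen outside folds | R², outside | R², inside |
|---|---|---|---|
| 44, correlation | 0.104 / 0.204 / 0.277 | 0.007 / 0.034 / 0.066 | −0.039 / −0.107 / −0.181 |
| 44, forest | 0.082 / 0.185 / 0.217 | 0.002 / 0.026 / 0.029 | −0.041 / −0.098 / −0.172 |
| 15, correlation | 0.042 / 0.113 / 0.137 | −0.005 / −0.001 / −0.007 | −0.028 / −0.066 / −0.123 |
| 15, forest | 0.011 / 0.056 / 0.078 | −0.010 / −0.019 / −0.034 | −0.027 / −0.072 / −0.125 |

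With the correlation screen outside the folds, r was 0.005 / 0.035 / 0.059 for a pool of 10 and −0.015 / −0.001 / 0.039 for a pool of 8. With the screen inside the folds, r was slightly negative throughout (−0.072 to −0.022).

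**Screening, weak true signal.** Three features each correlate 0.2 with the outcome, so the ceiling is √(3 × 0.04) = 0.35. Correlation screen, 120 runs.

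| Pool | r, outside | r, inside |
|---|---|---|
| 44 | 0.344 / 0.340 / 0.360 | 0.315 / 0.214 / 0.142 |
| 15 | 0.329 / 0.321 / 0.333 | 0.314 / 0.255 / 0.221 |

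**Which version is right?** Separately written code compared both with the true error in new patients (no signal, 50 features, outcome variance 1). MSE outside / inside / true was 0.99 / 1.02 / 1.02 at ICC 0.2, 0.98 / 1.09 / 1.08 at ICC 0.5, and 0.92 / 1.18 / 1.17 at ICC 0.8. Repeating the screen in each fold tracks the truth; screening once does not.

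**Forward chaining.** Training on earlier weeks and testing on the next (from week 5, 25 runs), screening once on all data changed r by 0.006 or less in a random-intercept model and by 0.005–0.04 in a pooled regression.

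**The case against.** Reusing the cross-validation for selection and for error is not in dispute. The case on the other side concerns the screen and the sizes.

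- **The harmful pipeline is not the one described.** Screened predictors go to hidden Markov and mixed models, for which forward chaining is the natural scheme, and there the leak is minor. A forest or SVM refitted without patient i carries no leak from the screen. This largely stands. But the plan does not say which scheme scores the mixed models, and leave-one-patient-out for them is not excluded.
- **Training on all but patient i can be read to include the screen.** It can, which is why this part is conditional. The two readings give different answers, and the plan does not choose between them.
- **A pool of 44 is the count before reduction.** Fair: the screen comes after unsupervised reduction. With 15 or fewer features R² outside the folds is at or below zero, so noise does not pass for skill. Even so, at 15 it is 0.02–0.12 better than the in-fold value with the correlation screen. The size after reduction is not given.
- **Selection optimism is small, and 12 candidates is an assumption.** The plan names about four model families, and at ICC 0.3 with 4 candidates the optimism is below 0.01. Tuning variants and alternative reductions could raise the count. The simulated candidates are linear stand-ins for the plan's models.
- **Aim 3 is model development.** True, and no effect on Aim 4 or on power is claimed.

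**Conclusion.** The concern holds. As written, the plan reports as generalization error the same quantity it minimizes to choose the model, so the chosen model's error is too favourable on average. The likely size is modest: 0.003–0.07 in R² with 4 candidates and up to 0.10 with 12, growing with within-patient correlation.

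The screening part holds conditionally. If the screen is run once on all patients and its predictors enter a model scored by leave-one-patient-out, the error is too low. The effect is clear with a pool of about 44 (pure noise gives r of 0.10–0.28 with a correlation screen, 0.08–0.22 with a forest screen) and close to nil with 8. Under forward chaining it is minor.

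The sizes rest on the assumed ICC, pool size, 5 kept predictors and linear models, none of which the documents fix. The direction does not depend on these choices. This should be fixed, but it does not invalidate the study.

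**What to change.** Amend the Aim 3 text of Data Analyses as follows.

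- Repeat every step that uses the outcome (forest/SVM screen, FDR threshold if it tests the assessments, tuning, choice of algorithm) using only the training data of each fold.
- For cross-sectional models, use patient-level nested cross-validation: select on the inner loop and report error from the outer held-out patients.
- For time-series models, screen and select using only times 1 to t−1 before predicting time t.
- State that the minimum leave-one-out MSE used for selection is not the reported generalization error.

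It would also help to state which models are scored by which scheme and what the FDR threshold tests, but these are clarifications. The cost is some SAP wording, more computing time and a somewhat less favourable reported performance. Data collection does not change.

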## Protocol

### Passive Mobile Self-Tracking of Mental Health by Veterans with Serious Mental Illness

NCT 05023252

April 29, 2020

This project studies passive mobile sensing with Veterans in treatment for serious mental illness (SMI). Data are used for self-tracking behaviors and symptoms. While passive mobile sensing has been feasible, acceptable and safe in patients with serious mental illness, these are studied for the first time in VA. Analytics are developed that use passive data to predict behaviors and symptoms. The project has these objectives:

1. Conduct user-centered design of passive mobile self-tracking to support Veterans' management of their mental health.
2. Study the feasibility, acceptability and safety of passive self-tracking of mental health that includes feedback of mental health status to the Veteran.
3. Use mobile sensor and phone utilization data to develop individualized estimates of sociability, activities, and sleep as measured by weekly interviews.
4. Study the predictive value of using data on sociability, activities, and sleep to identify exacerbations of psychiatric symptoms.

The informatics platform will capture an array of passive sensing data off participant's smartphone device to track metrics indicative of behavioral patterns and physiological well-being. These metrics are all passively collected, requiring no active user input, to minimize user burden and ensure maximal user participation in the study. Comparison data will also be collected in the form of weekly assessments conducted by research staff via telephone.

The project will perform statistical analysis on the data to find which short- and long-term features could be correlated with clinical status. These features include both short- and long-term behavioral data, i.e. what an individual has done recently and how their behavior has changed over time. To generate these long-term features, our team will perform time-series analysis on the data and find which parts of participants' daily lives have changed over the course of the study. We will compare these changes to surveys collected at different points throughout the duration of the research study. After generating the relevant features, we use machine learning techniques to study a classifier which predicts whether an individual is in a risk group or not.

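### Read plainly, the hidden Markov models take past staff-interview scores as inputs, so their error describes phone data plus interviews and should not decide the Aim 3 model as if it were passive performance

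*Combined protocol and SAP*

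**What the plan says.** The overview describes the phone metrics so: "These metrics are all passively collected, requiring no active user input". It gives the staff calls a separate role: "Comparison data will also be collected in the form of weekly assessments conducted by research staff via telephone". Objective 3 is to develop "individualized estimates of sociability, activities, and sleep as measured by weekly interviews", so the interview is the reference that the phone data must reproduce.

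Data Analyses, Aims 3 & 4, then describes the models:

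- Hidden Markov models predict current behaviors and symptoms "based on current features and past patients' behaviors and symptoms". The next sentence adds that "patients' behaviors and symptoms are hidden states that enjoy the Markov property".
- Mixed effects models are used "to predict patient behavioral assessments using selected features from the preliminary stage", allowing for within-patient correlation. No lagged score is named.
- Time-series validation: "models will be trained on times 1, ..., t-1, and evaluated on time t, for each time t".
- Cross-sectional validation: "models will be trained on all but patient i, and evaluated on patient i, for each patient i".
- The selected model is the one with the smallest LOOCV mean squared error. No other criterion is given.

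For the time-series models, the plan asks neither for an error with past interviews withheld nor for a benchmark that uses the last score alone.

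**The concern.** The weekly source of the behavior and symptom scores is the staff telephone interview. If past scores are inputs, the reference standard is also a predictor. The week-t error then belongs to a system made of the phone and an interview from the week before. Scores of this kind usually persist from week to week, so such a system can predict well even when the phone contributes little.

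The stake is the choice of the Aim 3 model. A single minimum-error rule would set an interview-fed hidden Markov model beside models that see only phone features. It would tend to favor the former because it has more information, not because it reads the sensors better. The winning error could then be taken as the performance of passive tracking.

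**Working it through.** **1. The plan's own figures.** The plan states power but no prediction error. With n = 70 and two-sided alpha 0.05, the Fisher z formula is power = Φ(atanh(r)·√(n−3) − 1.96).

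- r = 0.50: 0.549 × 8.185 − 1.96 = 2.54, power 99.4% (stated: over 95%).
- r = 0.35: 0.365 × 8.185 − 1.96 = 1.03, power 84.9%. An exact calculation gives 85.4% (stated: over 85%).

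Both are reproduced, and this point does not affect them. The two correlations serve below as sensor strengths.

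**2. What past scores contribute.** Assumptions: score variance 1, patient ICC 0.5, weekly autocorrelation φ = 0.5, and sensor noise independent over time. The documents give none of these. The correlation of successive scores is ρ = ICC + (1 − ICC)φ = 0.5 + 0.5 × 0.5 = 0.75. As a share of score variance:

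- current sensors alone: 1 − r²
- last score alone: 1 − ρ² = 1 − 0.5625 = 0.44
- both: 1 − (r² + ρ² − 2r²ρ²)/(1 − r²ρ²)

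At r = 0.50 the last formula gives 1 − (0.25 + 0.5625 − 0.28125)/(1 − 0.140625) = 1 − 0.618 = 0.38.

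| Sensor correlation r | Sensors alone | Sensors + last score |
|---|---|---|
| 0 | 1.00 | 0.44 |
| 0.35 | 0.88 | 0.41 |
| 0.50 | 0.75 | 0.38 |

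A useless sensor with last week's interview (0.44) beats current sensors at the plan's r = 0.50 without it (0.75). Over ICC 0.3–0.7 and φ 0.2–0.8, ρ runs from 0.44 to 0.94, and the useless-sensor error runs from 1 − 0.44² = 0.81 to 1 − 0.94² = 0.12. At the low-persistence end the ordering reverses (0.81 against 0.75), so the preference is a tendency and not a certainty.

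**3. Which feature of the plan causes it.** Simulation of 70 patients over 39 weeks (nine months), ICC 0.5, φ 0.5:

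| Model and validation | r = 0.50 | r = 0 |
|---|---|---|
| Current sensors, leave one patient out | 0.755 | 1.022 |
| Current sensors, forward | 0.746 | 1.006 |
| Sensors with sensor history, forward | 0.529 | 1.014 |
| Last score only | 0.438 | 0.437 |
| Sensors + last score | 0.383 | 0.437 |
| Sensors + patient intercept from past scores | 0.490 | 0.518 |

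Forward validation alone barely moves the sensor-only error (0.746 against 0.755). The gain comes from past scores, used either as inputs or through patient effects. At r = 0.50, withholding scores multiplies the error by 0.746/0.383 = 1.9 with current sensors, or 0.529/0.383 = 1.4 with sensor history.

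**4. Interviews that stop after eight calibration weeks.** Base assumptions: ICC 0.6, autocorrelation 0.6, sensors explaining 15% of within-person variance. Over weeks 10–39 the error is 0.241 with the last score, running mean and sensor, and 0.454 with the eight-week mean and current sensor. The ratio is 0.454/0.241 = 1.9. Three other settings (ICC 0.5–0.7, autocorrelation 0.4–0.7, sensor share 10–20%) give 0.430/0.311 = 1.4, 0.556/0.241 = 2.3 and 0.366/0.188 = 1.9. Giving the passive model sensor history lowers the base ratio to about 1.6. With history and autocorrelation 0.2–0.3, the ratio is 1.05 to 1.19. In the base case, past interviews with no sensor give 0.265, against 0.242 with the sensor.

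**The case against.** A reader might infer that the chosen model cannot run passively. The documents do not establish that. In a standard hidden Markov model the past state is inferred from observed features, and interviews are needed only for training. The hidden-state sentence supports that reading and the sentence before it does not. What stands is that the text is ambiguous and must be settled.

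A reader might also infer that every time-series model, or every reported error, has this problem. That does not hold either:

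- The past-score input is stated for the hidden Markov models only. The mixed models name only selected features, and past interviews enter only if patient-specific effects fitted to them are used for prediction, which the plan does not say.
- The cross-sectional leave-one-patient-out error uses no follow-up interviews from the tested patient, though baseline measures may enter.
- The Aim 4 primary analysis relates mobile features to symptoms.
- Training on earlier weeks says what the model is fitted on. Forward validation is not itself the fault.

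Finally, a reader might infer that the stated accuracy is much better than a user would get. The plan states no accuracy figure and no model has yet been selected. The size also depends on how well the passive model is built: with sensor history and weak autocorrelation the gap nearly closes. These objections narrow the point. They do not answer the plain wording of the hidden Markov input or the selection rule that ignores what each model was given.

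**Conclusion.** The point holds in limited form. On the plain reading, the hidden Markov error describes phone data plus weekly staff interviews, and a single minimum-error rule compares it with errors from models that hold less information. That sits badly with the interviews' declared role as comparison data, and the two adjacent hidden Markov sentences need reconciling.

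The size is illustrative. Without ongoing interviews but after eight calibration weeks, mean squared error is about 1.05 to 2.3 times the interview-fed value. The range rests on assumed ICC, autocorrelation, sensor share and use of sensor history. If the sponsor intends scores for training only, the remedy is a clarifying sentence. This is a cheap improvement.

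**What to change.** Reconcile the two hidden Markov sentences. State that interview scores train the model and serve as the reference, but are withheld as inputs at prediction, for the error on which the Aim 3 model is selected and reported as passive performance. Say that patient-specific effects fitted to past interviews count as inputs for this purpose, which settles the mixed models too.

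Report one-week-ahead error with past scores as secondary, beside a last-score-only benchmark that shows what the sensors add. Compare models only within the same information set. A fixed calibration period (for example eight weeks) may be added as a labelled sensitivity analysis for individualized use. It is a design choice and still needs eight interviews.

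Cost: a re-analysis of data the study already collects and a few sentences, with no new assessments. The headline error may be less favorable.

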generalization error. Quadratic loss will be used to evaluate prediction error. The selected model will be the one that minimizes LOOCV mean squared error.

In Aim 4, outcome data are collected weekly for each patient on three scales (psychosis, mania, depression). These scales each have a range of 1 to 7. The primary outcome will be the scale indicating the most severe symptoms in a 2-month window. We will evaluate the association between mobile data features identified in Aim 3 with this primary outcome using a mixed effects model to accommodate within patient data correlation due to repeated measures. Specifically, we will consider feature data from fixed time windows preceding the most severe symptoms. The outcome data distribution will be examined prior to model fitting, and an appropriate link function will be used in the mixed effects model.

Sample size and power considerations: In Aim 3, we extract features of mobile sensor and phone utilization data to estimate behaviors in the domains of sociability, activity, and sleep. The selected features should have a high correlation with behaviors to be a good estimate. Of 100 participants enrolled, assuming 30% attrition, we expect to have complete data on 70 participants (and substantial longitudinal data for a larger group). This sample size will provide over 95% power to detect a correlation of at least 0.50 at the significance level 0.05 using a two-sided test. In Aim 4, our inclusion criteria select for greater than average symptom risk, so we anticipate substantial symptoms. Previous research on 21 patients with SMI for a median of 134 days found that sensing data predicted symptom indicator scores with correlations in the range of 0.5 to 0.8. Given possible confounders, and since our sample may be more heterogeneous than prior research, the correlation in our study is anticipated to be lower than what was reported previously. With 100 enrolled, and assuming 30% attrition, we will have over 85% power to detect correlations of at least 0.35 between predictors of interest and symptoms assessments at the significance level of 0.05 using a two-sided test.

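### The Aim 3 time-series models are judged on absolute prediction error with no sensor-free benchmark, so the result cannot show how much accuracy comes from the phone data

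*Combined protocol and SAP*

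**What the plan says.** The relevant text is in Data Analyses, Aims 3 & 4.

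- **Hold-out for time-series models.** "For time series modeling, models will be trained on times 1, ..., t-1, and evaluated on time t, for each time t". Each tested patient's own earlier weeks are therefore in the training data. Only the cross-sectional models leave whole patients out.
- **Inputs.** "We will use hidden Markov models to predict patients' current behaviors and symptoms based on current features and past patients' behaviors and symptoms". The next sentence reads: "We view patients' features as observed states, and patients' behaviors and symptoms are hidden states that enjoy the Markov property". It is therefore unclear whether the past behaviors are interview scores or states inferred from the phone. The mixed models use selected features "while taking into account within-patient correlation in repeated measurements over time", without saying whether estimated patient effects enter the forecast. Static baseline measures, including symptoms and functioning, may also be added.
- **Criterion.** Quadratic loss, averaged over hold-outs. "The selected model will be the one that minimizes LOOCV mean squared error".
- **Evidence on sensors elsewhere.** One dimension-reduction step is a multiplicity-controlled screen: "The second dimension reduction strategy is to use FDR (false discovery rate) threshold". A preliminary stage will "evaluate cross-sectional associations between mobile data features and patient behavioral assessments". The sample-size text adds a standard: "The selected features should have a high correlation with behaviors to be a good estimate".

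No section names a patient-mean, last-value, history-only or baseline-only comparator, or any measure of added accuracy.

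**The concern.** Objective 3 concerns what can be estimated from sensor and phone-use data, and the section on data collected from the app plans to follow shifts over time. A bare MSE on later weeks of known patients answers neither question. Behavior scores may be fairly stable within a patient. If so, any model that knows the patient's level will show a low error, whatever the phone adds.

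The plan's other checks establish association, which is a different property. A feature that only marks a patient as generally active or generally withdrawn can pass all of them, yet add almost nothing once earlier scores are known. The reported error would still look good. If past interview scores carry the prediction, that accuracy would also not hold where no weekly interview is done.

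**Working it through.** **Inputs from the documents.** 100 enrolled with 30% attrition gives 70 patients. Weekly calls over 9 months give about 9 × 52/12 = 39 weeks. The reference correlation in the Aim 3 power statement is 0.50.

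**The plan's own figure.** Power for r = 0.50, n = 70, two-sided 0.05 is Φ(atanh(0.50) × √67 − 1.96) = Φ(4.50 − 1.96) = 99.4%. This agrees with the stated figure of over 95%, which is not in dispute.

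**Assumptions.** Outcome variance 1; ICC ρ from 0.1 to 0.7; lag-one weekly autocorrelation (AR) of within-patient deviations 0 to 0.4; forecasts from week 5 on, so m = 4 to 38 earlier weeks (35 forecasts).

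**Hand calculation at ρ = 0.5, AR 0.** Let y = u + e, with Var(u) = ρ for the patient level and Var(e) = 1 − ρ for the week.

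1. *History only.* MSE after m weeks is (1 − ρ) + ρ(1 − ρ)/[(1 − ρ) + mρ], which is 0.5 + 0.5/(m + 1). The average is 0.5 + 0.5 × (1/5 + … + 1/39)/35 = 0.5 + 0.5 × 2.170/35 = 0.531. The forecast-observed correlation is √(1 − 0.531) = 0.68 with no sensor at all.
2. *Weekly feature*, x = 0.5y + error of variance 0.75. The MSE is 1/(1/v + 0.25/0.75) with v = 0.531, that is 0.531/1.177 = 0.451. The reduction is 0.080.
3. *Stable-level feature*, x = u + error of variance 0.5. One reading tells as much about u as one more interview, so m + 1 becomes m + 2: 0.5 + 0.5 × (1/6 + … + 1/40)/35 = 0.5 + 0.5 × 1.995/35 = 0.5285. The reduction is 0.0025, before any cost of estimating coefficients.

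Both features have variance 1 and covariance 0.5 with y, so pooled r is 0.50 for each. On a left-out patient both give MSE 1 − 0.25 = 0.75. Neither check tells them apart.

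**Simulation of the same comparison** (rolling origin; the benchmark is a pooled regression on past scores):

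| Setting | Stable-level feature | Weekly feature |
|---|---|---|
| MSE, ICC 0.5, AR 0 (benchmark 0.534) | 0.536 | 0.453 |
| MSE reduction, ICC 0.4–0.7, AR 0–0.4 | −0.002 to 0.004 (95% half-width 0.002 to 0.010) | 0.021 ± 0.006 to 0.113 ± 0.022 |
| MSE reduction, ICC 0.3 | 0.013 to 0.016 | 0.104 to 0.147 |
| Patient-intercept mixed model v same model without sensors, ICC 0.4–0.7 | −0.018 to 0.000 | 0.027 to 0.108 |
| Left-out patients, ICC 0.4–0.7 (both features) | MSE 0.75–0.77, r 0.46–0.50 | MSE 0.75–0.77, r 0.46–0.50 |

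Half-widths are 1.96 × SD of the per-patient MSE difference/√70. In a separate check (200 runs, 5% false discovery rate, patient means, AR 0, ICC 0.4, 0.5 and 0.7), the stable-level feature passed the screen in every run. Its random-intercept coefficient was significant in 12% to 100% of runs, depending on ICC and error type.

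**Useless features.** Past scores plus five pure-noise features gave r 0.60 to 0.85 at ICC 0.4 to 0.7, and 0.50 to 0.61 at ICC 0.3. At ICC 0.1 to 0.2 they gave 0.22 to 0.38 with AR 0, and 0.46 to 0.54 with AR 0.4. Against the benchmark their MSE reduction was −0.006 to −0.002, correctly showing no gain. The screen would remove most such features: at least one of five survived in 7% to 10% of runs. The stable-level feature is therefore the case that matters.

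**The case against.** The strongest reply is that the quoted sentence is only a rule for choosing among candidates. Nothing says the MSE will be offered as proof of sensor value. Individualized estimates may properly use patient history, association is tested elsewhere, and what passes to Aim 4 is a set of features rather than an error figure. This is right about selection, and no harm to selection is claimed. But the hold-out error is the plan's measure of how well the Aim 3 time-series models perform, and it has no reference value.

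A second reply is that the mechanism depends on unsettled readings. If hidden states are inferred from the phone, or mixed-model forecasts use fixed effects only, much of the history effect disappears. The size would then change. Even so, an MSE without a comparator would not show the phone's share, and baseline measures could still contribute.

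The objections to the magnitude largely stand:

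- ICC and AR are assumed.
- No hidden Markov model was run, and baseline covariates were not simulated.
- The screening check used patient means, which the plan does not specify.
- The plan's 0.50 is a feature-behavior correlation, so a forecast-observed r is not the same quantity.
- A purely stable-level feature cannot have pooled r above √ICC. The value 0.50 therefore needs ICC of at least 0.25, and at ICC 0.3 such a feature does add a little.

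**Conclusion.** The concern holds. Under the criterion as written, the time-series error for Aim 3 cannot separate the contribution of phone data from stable patient scores, and the planned association checks do not fill that gap. At assumed ICC 0.4 to 0.7, two features with identical pooled correlation and near-identical left-out-patient error differ clearly in what they add: essentially nothing against 0.021 to 0.113 of an outcome variance of 1. At ICC 0.1 to 0.2 without autocorrelation, history alone predicts poorly and the masking is weak. These figures illustrate the mechanism and do not forecast this trial's results. Sample size, stated power and the selection rule are unaffected. This is a low-cost improvement to what Aim 3 can conclude.

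**What to change.** 1. For each domain, fit a no-sensor benchmark (baseline covariates plus past interview scores) and score it on the same held-out weeks and outcome scale as the selected model.
2. Report the MSE reduction against that benchmark with an interval computed at patient level.
3. For the left-out-patient models, use a baseline-only or grand-mean benchmark.
4. State whether past states in the hidden Markov model are interview scores or are inferred from phone data, and whether patient effects enter the mixed-model forecast. If interview scores are used, also report the error without them. That version would show the value of a stable-level feature where no interview history exists.

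The minimum-MSE selection rule can stay as written. The cost is some SAP wording and a few extra fits on data already collected. The one drawback is that the headline accuracy may look less favorable.
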